Surprisingly, while there is literature documenting the dependence of the skin temperature on air temperature, this was somehow forgotten in the first implementations of thermographic fever screening systems and subsequently the international standard developed and promulgated for this purpose. It is unclear how a thermographic system that does not account for environmental air temperature changes could produce accurate core body temperature measurements. Further, there is very little literature on the impact of these potential confounds on thermographic body temperature measurement methods (e.g. see Fig 2 in Obermeyer et al for correlates between oral core body temperature and pulse, blood pressure and weight/BMI). This is relevant for public health, since at this time, non-contact body temperature measurement is used widely not only by some clinical practices but also by public and private organizations for assessing individuals for the presence of possible fever. Early in 2020, retrospective studies on hospital admissions in China showed fever to be the single most common initial indication of infection with SARS-nCov-2 (Guan et al). Later studies revealed the presence of considerable asymptomatic and presymptomatic transmission, lowering the risk reduction possible for COVID-19 using temperature screening. The lack of research on the science of non-contact body temperature measurement and more importantly the lack of a method to assess the real-world sensitivity and specificity of such systems provides credence to the claim that much, if not all, of non-contact body temperature measurement for COVID-19 is mere “safety theater”, implemented with less regard to actual utility in detecting febrile individuals than to the appearance of providing safety.

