transparent to visible light. Also note the subject's left inner canthus is delineated on the image to the left with white specks (the hottest subset of pixels is replaced by white to provide feedback on device operation). The inner canthus is not the eye nor the tear duct, but rather a space on the nasal bridge midway between the eye and the nasion, very close to where eyeglasses with metal wire bridges terminating in a flat soft pad would contact the nasal bridge.

The overall goal of this study is to improve the IR thermometry science by 1) contributing a method for the objective manipulation of face temperatures using environmental air temperature changes and 2) developing a schema to use this method to assess the real-world sensitivity and specificity of non-contact IR core temperature measurement systems in normal, mild, moderate and severe fever groups, corresponding to core temperatures below 38C (100.4F), 38-39C (100.4-102.2F), 39-40C (102.2-104F) and above 40C (104F). This study is relevant for public health risk, because at present, there is no real-world objective test for thermographic febrile temperature screening devices, which significantly hampers the ability of regulatory authorities to identify improperly operating devices. A secondary goal is to determine the impact of potential confounds on non-contact thermographic temperature measurement. This translates to clinical utility, as any confounds could influence the decisions to prioritize the use of such systems. This is also related to public health risk, because the non-contact core body measurement systems the public is now relying on may have unacceptable biases in their determination of core temperature and it is possible they may even induce harm by altering behavior. Additional documentation is provided as a supplement for the review of this study detailing methods for the evaluation of thermographic systems.

B. Research Design and Methods

Study Population

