Exclusion criteria

1. Contraindication to oral temperature measurement.
2. Inability to follow instructions.
3. Any diagnosis associated with abnormal core thermoregulation, e.g. autonomic dysfunction.
4. Obvious signs of tissue damage present in either inner canthus.
5. Facial artery abnormality if previously diagnosed.
6. Experienced discomfort while receiving most recent clinical oral thermometry measurement.

Study Procedures

After a detailed explanation of the study and its potential risks and benefits and informed consent will be obtained by the principal investigator or one of the co-investigators. Participants will then receive a single printed sheet containing places to enter the demographic and clinical information outlined above, as well as an NFC sticker uniquely linking the information on the sheet to all temperature measurements (Data Collection Sheet included in protocol materials).

The total time involved for participants will be approximately 120 minutes, with 100 minutes being spent in actual study procedures. The oral and thermal imaging evaluations will be performed in rooms identified as suitable for the purposes below. There are two separable phases to the study, the first (**blinded temperature phase**) involves isolated non-contact measurements and oral thermometry in a building-temperature room after spending ten minutes in each of three blinded elevated-temperature rooms and the second (**equilibration phase**) involves serial non-contact measurements of the inner canthi of seated participants over ten minutes and an oral thermometry measurement in one elevated temperature room and one reduced temperature room. All study procedures will be performed in groups sized no larger than allowed by St. Olaf College's COVID-19 restrictions on social distancing within the selected rooms. Participants will receive a \$20 gift card in compensation for their time and effort involved in participation in this study.

[figure not shown]
Oral Thermometry

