encompassing both areas. The desired target temperatures for the equilibration phase (Rooms D and E above) are 60F and 80F (or 10F lesser than and 10F greater than the building's setpoint), while the desired target temperatures for the blinded temperature phase (Rooms A, B and C) are 68, 75.6 and 83.2F, if the building's target temperature is 68F, otherwise these should be offset with the difference. To obtain these temperatures, three rooms require heating and one room requires cooling. Each of the heated rooms will have a 1500W space heater and the cooled room will have a flexible temporary doorway installed with ductwork to a portable air conditioning unit. A wall-powered thermostat directed to switch by a rectified PID controller is then used to regulate the on/off cycle of each system. The building's airflow via the ductwork into the room may be damped with assistance from building maintenance. An air temperature logging system is set up in each room and in a preliminary study, is used to obtain the time constant and thermal stability of the room with the associated heating and cooling equipment. The key requirement for a suitable room is that the thermal stability must remain within 1C (1.8F) of a single value near the desired setpoint temperature for 10 minutes. Note, during both phases, it is unlikely these exact setpoints will be achieved at all times due to repeated opening and closing of doors, but fortunately this is not essential because ultimately the analysis is dependent on induced surface temperatures and the resulting induced core temperatures will be calculated for each subject based on the actual blinded temperature and the temperature of the room the IR thermometry is done within.

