The rooms will each consist of a portable tent with dimensions of at least 5x5ft base and height of 6ft. The critical requirement of said tent is sufficient thermal isolation from ambient temperatures to allow the maintenance of the required elevated or cooled temperature setpoints to within 1.8F. At present time, the most suitable tent is the THUNDERBAY Ice Cube 3 Man Portable Ice Shelter <https://www.amazon.com/gp/product/B019CU59VI>. This tent is surprisingly large, and has sufficient space to allow four adults to stand with 2 feet between adjacent people or two people with over 3 feet between them. The thermal radiant intensity of the walls of this tent do not match that of the elevated or cooled air temperature, because these walls directly contact and conduct to the ambient air and equilibrate between the ambient and internal temperatures, thus they radiate closer to the ambient temperature. Therefore, additional radiating membranes are used, consisting of sheets of fabric or paper hung from the ceiling or otherwise mounted with at least several inches displacement from the walls and having sufficient but low level of air flow to equilibrate the majority of the membrane to the internal air temperature. A GFCI-protected extension cord and powerstrip will be used to provide power to each tent.

The formula relied upon to obtain the ideal elevated temperatures is as follows, given as a lambda expression, which incorporates a first lambda (Python):

- $core2surf = \lambda core, air: core - (core-air)*0.191$

- $get_needed_room_air = \lambda air, febrile: core2surf(febrile, air) - ((98.6 - core2surf(febrile, air))/0.236)$

This gives us the needed heating temperature to get a desired change in body temperature, e.g. $get_needed_room_air(68, 100.4)$ returns 75.6F, meaning, in order to simulate a 100.4F core

temperature, a person must equilibrate to 75.6F air temperature before returning to receive a scan from the primary scanner located in 68F air temperature. This can be summarized more simply as, for every 1C (1.8F) elevation desired, the heated room must be that multiple of 4.23C (7.62F) above the scanning area's air temperature. Note, the exact coefficient was determined in a pilot study performed in June 2020, and may be refined by this study, which could alter the expected induced core temperatures.

Detailed Procedure - Blinded Temperature Study

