Once the break time is concluded for each subject, the process switches to the equilibration time measurement. Participants will wait an extra six minutes before proceeding to one of the rooms, in alternating order, so after ten minutes, the participant simply switches to the other equilibration room. A spreadsheet demonstrating the sequencing is included in the protocol materials, showing the time (10:00AM is selected as the start time for demonstrative purposes) in two-minute increments for 100 minutes, the participant (out of nine) who is currently switching rooms, the room they are being sent to (lettered A-E), which person is receiving the

thermographic scan, which person is receiving an oral measurement and the number of people at any given time in each room.

C. Safety

The risk to the participants participating in this study is low. Thermal imaging is a non-invasive, completely passive procedure. We do not expect any discomfort associated with thermal imaging. Oral thermometry is considered to have no risk, but it is possible participants could experience discomfort with oral thermometry. If participants indicate severe discomfort, the operator will immediately discontinue the procedure. The majority of the population has received a clinical oral thermometry procedure and participants are only eligible if they have received a clinical oral thermometry procedure in the past.

D. Analyses

It is foreseen that the two types of data will be analyzed separately and in two ways each. The equilibration data will be analyzed to determine the physiologic time constant in each dataset and grouped by direction of equilibration (heating, cooling). The groups of time constants will be assessed for significant differences between heating and cooling by two-sample t-test and a 95% confidence threshold. The average and standard deviation time constant (and if these are significantly different, this will be performed separately for heating and cooling) will be recorded and reported in an open-access publication with the rest of the results. The endpoint of each equilibration dataset will also be used to determine a linear physiologic offset (note, the existing parametric physiologic offset was previously determined in a 32-subject sample in June 2020 but for the purposes of this study, we intend to re-evaluate this equation) and the resulting equation and coefficients published along with the equilibration results.

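### Sensitivity and specificity are measured at one scan-area air temperature, so they cannot separate a system that corrects for ambient air from one with a fixed calibration suited to that temperature

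*Combined protocol and SAP*

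**What the plan says.** The Introduction faults systems that take no account of air temperature: "It is unclear how a thermographic system that does not account for environmental air temperature changes could produce accurate core body temperature measurements". It also criticises the international standard for not addressing how the ideal threshold moves with ambient air. Its overall goal is a schema to "assess the real-world sensitivity and specificity of non-contact IR core temperature measurement systems".

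Section B, Study Procedures, describes the blinded phase: it "involves isolated non-contact measurements and oral thermometry in a building-temperature room after spending ten minutes in each of three blinded elevated-temperature rooms". Controlled Temperature Rooms gives the targets, "Rooms A, B and C) are 68, 75.6 and 83.2F", and describes the participant as returning to "receive a scan from the primary scanner located in 68F air temperature". Secondary Non-Contact Equipment places the other systems next to the primary one. Section D draws the sensitivity and specificity of every system from these controlled-face-temperature data.

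Scan air is varied on purpose only in the equilibration phase, in Rooms D and E. The Equilibration Study procedure names only the primary camera there, with an oral reading at the end of each room. Section D uses these data for time constants, and adds: "The endpoint of each equilibration dataset will also be used to determine a linear physiologic offset". It plans no comparison of the existing equation's core estimate with oral temperature at each air temperature.

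**The concern.** A participant warmed in Room B or C and scanned at the setpoint is meant to present the same skin temperature as a febrile person scanned at the setpoint. That tests whether a system tracks face temperature. It does not test whether the system handles a change in the air around the scan, because that air does not change. A system whose calibration is frozen at the setpoint could score well and then misread people in a warmer or cooler room.

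The stake is the scope of the published claim. Sensitivity and specificity at one ambient would be reported as real-world performance, in a study whose title and motivation concern environmental temperature. For the primary system, the data that could test its ambient correction are collected, but the plan assigns them to refitting that correction without first scoring the existing one.

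**Working it through.** **Inputs**
- Skin model (Controlled Temperature Rooms): surface = "core - (core-air)*0.191", that is, 0.809 × core + 0.191 × air.
- Inverse slope: 0.191/0.809 = 0.236, the second constant in the same section.
- Scan-area air 68F; Rooms A, B, C at 68, 75.6, 83.2F (same section).
- Rooms D and E: given there both as 60F and 80F and as 10F either side of the setpoint.
- Oral mean 97.9–98.6F, SD about 1F (Introduction). SDs for readings: 0.48F and 1.11F (Population Size).
- Assumed: the algorithms below. The documents do not describe those of the secondary systems.

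**Reproducing the plan's figures.** For a 100.4F core in 68F air, surface = 100.4 − 32.4 × 0.191 = 94.21F. Needed room air = 94.21 − (98.6 − 94.21)/0.236 = 75.6F, as stated. The same steps for 102.2F give 83.2F, as stated. The rule that "the heated room must be that multiple of 4.23C (7.62F) above the scanning area's air temperature" also follows: 1.8/0.236 = 7.63F.

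**Readings at 68F, true core 98.6F.** Surface temperatures after Rooms A, B and C are 92.76, 94.21 and 95.66F. Three systems are compared:
- Correcting: (surface − 0.191 × actual air)/0.809.
- Fixed map: the same equation with air frozen at 68F.
- Constant offset: surface + 5.84F, which is right for 98.6F at 68F.

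| System | After A | After B | After C | At or above 100.4F after B (SD 0.48 / 1.11) |
|---|---|---|---|---|
| Correcting | 98.60 | 100.39 | 102.19 | 50% / 50% |
| Fixed map, 68F | 98.60 | 100.39 | 102.19 | 50% / 50% |
| Constant offset | 98.60 | 100.05 | 101.50 | 23% / 38% |

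The first two rows are identical. A fixed map tuned to 72F (assumed) reads 0.236 × 4 = 0.94F low and puts 2% or 20% above 100.4F after Room B, so it does not tie.

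**Error of the tying system elsewhere.** Its reading is (0.809 × core + 0.191 × air − 0.191 × 68)/0.809 = core + 0.236 × (air − 68), whatever the core temperature.
- Rooms 10F either side of the setpoint: 0.236 × 10 = ±2.36F.
- Rooms at 80F and 60F with a 68F scan area: 0.236 × 12 = +2.83F and 0.236 × 8 = 1.89F low.

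**Healthy people flagged at 100.4F in the warm room**, with core ~ N(m, 1):
- Error +2.36F: the effective cut is 98.04F. For m = 97.9, 1 − Φ(0.14) = 44%; for m = 98.6, Φ(0.56) = 71%.
- Error +2.83F: the effective cut is 97.57F. For m = 97.9, 1 − Φ(−0.33) = 63%; for m = 98.6, Φ(1.03) = 85%.
- At the setpoint: 1 − Φ(2.5) = 0.6% to 1 − Φ(1.8) = 3.6%, the same as for a correcting system.

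In the cool room a true 102.2F core reads 102.2 − 1.89 = 100.31F or 102.2 − 2.36 = 99.84F, below the fever cut either way.

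**Could incidental drift reveal it?** Air temperature is stored for each scan. Borrowing the 1.8F stability tolerance, the error is 0.236 × 1.8 = 0.42F, which is small, and no planned analysis looks for it.

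**The case against.** Holding scan air constant while varying face temperature is a legitimate one-factor design, and the failure that the face-manipulation test is explicitly built to detect is bias-to-normal. One air temperature can still reveal that: Section D contrasts about 50% above threshold for a good system with perhaps 10% for a biased one. A reader might infer that the blinded phase misses its own target. The documents do not support that; neglect of ambient air is a stated motivation, not the declared target of this test.

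A reader might also infer that any system ignoring air temperature would pass. It would not. The tie needs both the right slope and tuning to the actual scan-area air; a constant offset, or tuning to another ambient, scores visibly worse. What remains is that a good score does not exclude ambient neglect and a poor score does not identify it.

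Nor does refitting the offset destroy the test of the existing equation. Thermographs, air temperatures and oral readings are kept, the new coefficients are to be published, and comparing them with 0.191 is itself a partial check. What is missing is a prespecified check against oral temperature before the refit.

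Finally, taking every secondary system into Rooms D and E is not shown to be feasible. The documents do not say the devices are portable, manual logging relies on a number shown after a primary scan, and participants move directly between the two rooms.

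**Conclusion.** The point holds as a limit on what the results can claim and as a missing analysis. It does not invalidate the blinded phase. At the setpoint, a suitably calibrated fixed-map system is indistinguishable from a correcting one. Away from it, that system errs by about ±2.4F, or by +2.8F and −1.9F, depending on how the targets for Rooms D and E are read. The share of healthy people flagged in the warm room is then about 44–71% or 63–85%, against 0.6–3.6% at the setpoint.

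These figures rest on the protocol's linear model, full equilibration, oral mean 97.9–98.6F with SD 1F, no added device noise, and a hypothetical device. They are not predicted errors for any named system or any planned result. The range itself reflects an inconsistency to reconcile: 60F and 80F are 10F either side of 70F, while Rooms A to C are set for 68F.

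**What to change.** 1. In Section D, equilibration analysis, add a step before any refit. Lock the June 2020 equation and apply it, with the logged air temperatures, to the primary system's endpoints in Rooms D and E and its scans after Room A. At each of the three air temperatures report core estimate minus oral (mean and SD) and the fraction at or above 100.4F. Then refit as planned. This costs nothing in data collection, since everything needed is already recorded.

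2. In the overall goal of the Introduction and in the sensitivity and specificity paragraphs of Section D, state each system's results as holding at building-setpoint air temperature, and drop the real-world description. The cost is a narrower claim.

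Optionally, take a reading with secondary devices at the end of Rooms D and E and report the same two quantities, but only if portability, record linkage and the schedule allow.

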Each participant is given a random room letter provided by a display configured to output a letter randomly pulled from a uniform distribution of the room numbers A, B and C. The participant is to go to said room and locate the NFC scanner inside and scan their data collection form to obtain their **nfc-room-scan** (to be used in later identifying which temperature group their body is simulating). Once the participant has entered a room, the door to the room is closed and the participant is instructed to wait while remaining relatively still for ten minutes while avoiding touching their faces and avoiding stressful content (e.g. avoid browsing the internet). At the conclusion of the ten minutes, determined by study personnel, the door will be opened and the subjects will exit the room and walk to the scanning area to scan their data collection form to obtain their **nfc-temperature-scan** and receive three consecutive face scans. After these scans are complete, participants will proceed to additional thermographic face scanning equipment to receive additional scans within one minute of exiting the equilibration room. Study personnel will record the results of any additional equipment scans along with a unique number displayed on the primary thermographic system display at the conclusion of their primary temperature scan. Study personnel will then obtain an oral thermometry measurement. After all oral and IR thermometry measurements are complete, participants will proceed to the next blinded temperature room and the above process is repeated. This is repeated until all participants have received scans after spending ten minutes in all three blinded temperature rooms, at which point they proceed to one of the equilibration rooms, described below.

Detailed Procedure - Equilibration Study

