Each participant is directed to go to one of two rooms (labelled D or E, used for *heating* or *cooling*), enter as directed by a study personnel, scan their NFC sticker to enable their **nfc-equilibration-scan**, and subsequently sit in front of the primary thermographic system for 10 minutes. The subject may freely close their eyes and move around as long as their eye locations are visible by the camera system, which is aided by instructions provided by the operator to "ensure that at nearly all times you can see the lens of the thermal camera", with a picture as below posted nearby. At the conclusion of the serial measurement, study personnel will obtain an oral thermometry measurement. This process is repeated in the second room.

You may move around and close your eyes freely but please make sure both eyes are in view of the thermal image lens (see arrow) at all times.

Periodically check that you can see the entire ring (red circle) with both eyes.

Timing of Study Procedures

By appointing five rooms and interleaving equilibration times with scan times, it is possible to complete all measurements above on 9 subjects in 94 minutes, plus up to a 15-minute break in the middle of procedures. Briefly, every two minutes, one of the nine subjects is given a letter, whereupon they proceed to said lettered room to wait for 10 minutes to equilibrate for the blinded portion. The random letter drawing process is balanced so at most times, there are no more than 2 subjects in the room at a time. After the ten minutes is complete for a participant, study personnel will direct the participant to the scanning area. A third of the time, a new participant will be entering about the same time as a participant is leaving the room. The participant obtaining a scan will walk to the scan area, receive their primary scan, then any secondary scans, requiring a total of two minutes. Then the participant will receive a monitor-mode oral temperature, requiring up to two minutes. There will be approximately 4 minutes between this time and when the participant should go to the next lettered room for a ten minute equilibration time. This process repeats until all three rooms are complete, at which point the subjects are given an opportunity to have a break for up to 15 minutes. Note, we will interview subjects at the start of their break time and if they wish to begin sooner than 15 minutes and if the sequencing permits, the subject may proceed with less than a 15 minute break.

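### The room-letter draw is described in two different ways, no balancing rule is stated, and nothing balances the order in which Rooms A, B and C are visited

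*Combined protocol and SAP*

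**What the plan says.** Section B, Detailed Procedure - Blinded Temperature Study, assigns rooms by "a display configured to output a letter randomly pulled from a uniform distribution of the room numbers A, B and C". It states no exclusion of rooms already visited and no limit on occupancy. The same paragraph sets the end condition: "This is repeated until all participants have received scans after spending ten minutes in all three blinded temperature rooms".

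Section B, Timing of Study Procedures, describes the same step differently: "The random letter drawing process is balanced so at most times, there are no more than 2 subjects in the room at a time". It does not say how this is achieved. The timetable is that "every two minutes, one of the nine subjects is given a letter, whereupon they proceed to said lettered room to wait for 10 minutes".

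Three other places bear on the point:
- Timing of Study Procedures refers to a spreadsheet in the protocol materials that shows, in two-minute steps, who moves, to which room, and how many people each room holds. It is not part of the text reviewed.
- Controlled Temperature Rooms gives the tent capacity as four adults standing 2 feet apart, or "two people with over 3 feet between them".
- Section D labels each scan from the air temperature of the room just left minus that at the scanner. Visit number does not enter.

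**The concern.** The uniform draw is the only operational instruction for assigning rooms. Taken alone it does not produce the plan's own end condition, and it does not produce the occupancy that the timetable describes. Someone programming the display from that sentence would build something other than what the timing section assumes.

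The only balancing mentioned concerns occupancy. Nothing balances which room comes first, second or third. The first visit follows whatever the participant was doing before the session. Later visits follow another room after about eight minutes (2 for scans, up to 2 for oral thermometry, about 4 waiting). How much carries over depends on the physiologic time constant, which this study itself sets out to estimate. With 28 participants required and up to 45 recruited, chance imbalance in order is plausible, and Section D has no term for it.

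**Working it through.** **Inputs, all from Timing of Study Procedures.** Nine subjects; one entry every 2 minutes; 10-minute stay; 2 minutes for the primary and secondary scans together; at most 2 minutes for oral thermometry; about 4 minutes' wait before the next room; a six-minute wait before the equilibration phase; 94 minutes in total, excluding the break.

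**1. The plan's own figure.** One cycle is 10 + 2 + 2 + 4 = 18 minutes. The ninth subject starts at 8 × 2 = 16 minutes and ends the blinded phase at 16 + 2 × 18 + 10 + 2 + 2 = 66. Adding 6 + 10 + 10 + 2 gives 94 minutes, an exact match. The timetable therefore assumes exactly three room visits per person, with no repeats.

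**2. A plain uniform draw (independent, with replacement).**
- All three rooms in three visits: 3!/3³ = 6/27 = 22.2%, or 2 of 9 people per session.
- Exactly two different rooms: 18/27 = 66.7%. The same room three times: 3/27 = 11.1%.
- Mean visits needed to see all three rooms: 3 × (1 + 1/2 + 1/3) = 5.5. That is 5.5 × 18 = 99 minutes, against 3 × 18 = 54 for three visits.

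**3. Occupancy.** At steady state 10/2 = 5 people are in the rooms. Two or fewer in every room requires a 2-2-1 split: 3 × 5!/(2! 2! 1!) = 90 of 3⁵ = 243 arrangements, or 37.0%. Some room holds three or more for the other 63.0%.

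**4. Without replacement, no occupancy rule.** Everyone now sees all three rooms. Occupancy does not improve: the five people present are always five different people, each equally likely to be in any room, so step 3 applies unchanged. A simulation of 20,000 sessions gave 37.0% of slots at two or fewer.

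**5. Without replacement, with an occupancy rule.** The rule here is an assumption, since the text states none: draw among unvisited rooms holding fewer than two people, otherwise take the least occupied unvisited room. In 20,000 simulated sessions:
- all nine people completed all three rooms, and each letter kept probability 1/3 in every visit period;
- every room held two or fewer in about 88% of steady-state slots;
- 15,748 sessions (79%) still had three or more people in a room at some point.

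In a further simulation of the same rule, the nine first visits split 3-3-3 in only about 25% of sessions.

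**6. Fixed rotations on the same timetable.** ABC, BCA, CAB repeated three times, and ACB, CBA, BAC repeated three times, were each checked entry by entry. Both take every participant through all three rooms, never put more than two in a room, and use each room three times in every visit period. This counts a room as vacated at 10 minutes. If the person entering arrives before the person leaving has gone, a third is briefly present at 8 of the 27 entries.

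| Assignment | Complete all rooms in three visits | Steady-state time with every room at two or fewer |
|---|---|---|
| Independent uniform | 22% | 37% |
| Without replacement only | 100% | 37% |
| With assumed occupancy rule | 100% | about 88% |
| Fixed rotations | 100% | 100% |

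**The case against.** A reader might infer that neither the three-room visits nor the schedule can be run as written. The documents do not support that. Nowhere do they say that draws are independent or with replacement. Study Procedures, the detailed procedure and the timing section all require every participant to visit all three rooms. The 94 minutes reproduces with three visits each. A restricted random draw can keep each letter at probability 1/3 and still hold rooms to two most of the time, so uniform and balanced are not contradictory in principle. The spreadsheet may already contain a balanced sequence.

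A reader might also infer that crowding breaks the tent spacing. That is weak. The two-person figure is qualified as usual rather than absolute, the tent takes four adults at 2 feet, and no numerical distancing limit is given. Room A may also form part of the main building-temperature area. Then only B and C matter, and even under the plain draw the chance of three or more in one of them is 2 × 51/243 = 42%.

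Nor do sensitivity and specificity rest on a paired contrast between rooms: Section D labels each scan from its own room and counts correct and incorrect labels. Random order also protects against systematic order bias on average.

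All of this stands. What remains is that the balancing rule is not stated, that drawing without replacement alone would not deliver the described occupancy, and that visit order is left to chance with no adjustment. An illustrative spreadsheet does not replace a stated assignment rule.

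**Conclusion.** The point holds as a specification gap that should be fixed, not as a bar to running the study. The two sections describe the room assignment differently. The literal draw gives 22% completion in three visits, and a draw without replacement but with no occupancy rule leaves some room at three or more 63% of the time. An occupancy rule brings the draw into line with the timing section but still leaves first visits unbalanced in about three sessions in four. The 22% and 63% are exact for the draws stated. The 88%, 79% and 25% depend on the assumed occupancy rule. The size of any order or carryover effect cannot be estimated from the documents. The conclusion could soften if the spreadsheet fixes the sequence.

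**What to change.** Reconcile the detailed procedure, the timing section and the spreadsheet. Delete the uniform-draw sentence and assign rooms from pre-printed sequences by participant number:
- one session: ABC, BCA, CAB, repeated three times for participants 1 to 9;
- the next session: ACB, CBA, BAC, repeated three times.

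Randomise which person receives which number, and keep the list away from whoever assigns fever groups in the blinded analysis. Record visit number and include it in the Section D analysis of the controlled face temperature data.

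The cost is one rewritten paragraph, a printed list and a small addition to Section D. No participants, session time or equipment are added. There are three drawbacks:
- The set of orders is tied to session. Within one session each room is preceded by only one other room, or comes first.
- An odd number of sessions leaves the six orders unequal. With 45 participants in five sessions of nine, three orders would have 9 people each and three would have 6.
- A session with fewer than nine people loses the exact 3-3-3 balance.
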